F. Power Analysis

We estimated sample size based primarily on Specific Aim 1. We estimated power to detect effects using G*Power and Optimal Design (for multilevel data), with $\alpha = .05$ and power $(1 - \beta) = .80$, completing 10,000 replications per analysis. With a conservative estimated dropout of 20% across conditions, though no dropout occurred in our pilot work, we will have power to detect moderate to large effects of condition on outcomes at post-treatment ($d = 0.72$) with 30 per group, and ($f^2 = 0.28$) with generalized linear models (GLM),

both large effects. For repeated measures analyses, with 4 data points, 30 per group with 20% missing data, we will be able to detect medium effects ($d = 0.60$) on change over time. These effect sizes are well below the observed effects in our pilot work ($g = 0.76$ to $g = 3.22$). For Specific Aim 2, the same power calculations for Aim 1 apply; however, tests of indirect effects are exploratory, we will be powered to detect a moderate indirect effect ($a*b = 0.25$), using the same constraints as above. To balance feasibility and ability to detect meaningful effects, we will recruit 30 individuals per treatment group

G. Analytic Strategy

Data will be screened for accuracy, missing values, and fit between the data and the assumptions of the general linear and linear mixed-model analysis (e.g., linearity, multivariate normality, independence of errors; Tabachnick & Fidell, 2007). Data transformations or model respecifications will be performed for any violated assumptions. We will implement pattern-mixture models to examine whether the missingness can be considered ignorable. For non-ignorable missing data, values will be multiply imputed and data recombined using Rubin's rules (Rubin, 1987) in the mixed model program. We will examine associations between primary dependent variables and factors such as gender, age, time since trauma, etc. and make appropriate analytic adjustments. We will test all covariate by predictor interactions to ensure our main effects are independent of the level of these putative covariates; these tests of effect modification are easily accommodated. However, we are underpowered to assess these interactions. To account for subjects being nested within groups in the treatment condition, we will co-vary treatment group using dummy codes in all analyses, as linear mixed models are difficult to estimate when the number of clusters is very small (Snijders, 2005).

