Specific Aim 1: Therapeutic Effects

Hypothesis: Those in Islamic Trauma Healing will show a greater reduction of PTSD symptoms and related psychopathology than those in the waitlist condition (WL).

Predictor Variables: Predictor is treatment (Islamic Trauma Healing vs. WL)

Dependent Variables: PTSD severity (PS-SR-5, primary outcome), depression (PHQ-9), somatic symptoms (PHQ-15), and well-being (WHO-5) will be measured.

Analyses: Because of the presence of clustering (participants in groups, observations over time, and participants in random assignment clusters), we will use generalized linear mixed models (GLMMs), which can account for the presence of clustering in data with varying distributional forms. We will compare pre-post GLMMs with those using data from all four time points to estimate the effects of treatment on both the level of the outcome at post-treatment, as well as change over time. To account for clustering (in treatment groups and random assignment clusters), we will include random intercepts for both treatment group and cluster (for those choosing to be randomized in a cluster). Because the waitlist control and non-clustered individuals will *not* be in a cluster, we will use the method outline by Sterba and Bauer (2008) to model random intercepts for *only* those in treatment or a cluster, and test whether modeling residuals as a function of clustering status appropriately models heteroskedasticity of residuals across clustering status. To test models of change over time, these models would be extended to three level models, with random intercepts and random coefficients for time-varying covariates (e.g., time) specified at Level 2 if the model fit is better than a fixed effects model.

Dropout. We will compare the percent of those who drop out of Islamic Trauma Healing to WL using a chi-square test. Reasons for dropout will be documented and compared across groups. Psychopathology and functioning of dropouts will be compared, using chi-square or *t*-tests, as appropriate.

Satisfaction. Means and standard deviation of satisfaction (CSQ) will be reported. A comparison to WL does not make sense, as there are no services with which to compare.

Specific Aim 2: Potential Mediators Change with Active Intervention

Hypothesis: Those in Islamic Trauma Healing will show a greater reduction of negative beliefs (PTCI), connectedness (SC; DSES), and/or forgiveness (TRIM-R) than those in the waitlist condition (WL).

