Predictor Variables: Predictor is treatment (Islamic Trauma Healing vs. WL)

Dependent Variables: Negative beliefs (PTCI), connectedness (SC; DSES), and forgiveness (TRIM-R) will be measured.

Analyses: We will conduct similar analyses to Aim 1, using both GLMs and GLMMs to obtain effect size estimates. In the GLMs, treatment will predict negative beliefs, connectedness, and forgiveness from baseline to post-treatment (controlling for baseline levels). GLMMs will be conducted as above, and treatment will be used to predict post-treatment levels and change over time in the dependent variables, to estimate how groups

STUDY PROTOCOL: A Lay-Led Intervention for War and Refugee Related Trauma: NCT03502278
July 18, 2018

differ in their rate of symptom reduction over the course of treatment.

Exploratory Hypothesis. Changes in negative beliefs (PTCI), connectedness (SC; DSES), and/or forgiveness (TRIM-R) will mediate the relationship between treatment condition and changes in PTSD and related symptoms. For the GLMs, we will predict Session 3 mediators from treatment (a path) and follow-up outcomes from the mediator (b path) controlling for treatment and baseline levels. Mediation will be tested using the product of coefficients method with bootstrapped standard errors (MacKinnon et al., 2009). In the GLMMs, we will conduct a 2-1-1 mediation, predicting the mediator at all time points from treatment (2-1), and the outcome at all time points from the mediator (1-1), controlling for treatment. This will be based on Bauer et al. (2006), generally following the product of coefficients method. It is recognized that this is underpowered.

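### The Aim 1 mixed models state no baseline adjustment, and site enters neither the randomisation nor any model of this two-city trial; both cost precision that can be recovered cheaply.

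*Combined protocol and SAP*

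**What the plan says.** **Baseline.** Specific Aim 1 lists treatment as the sole predictor of PS-SR-5. Its analysis sentence reads "We will compare pre-post GLMMs with those using data from all four time points to estimate the effects of treatment" and continues "on both the level of the outcome at post-treatment, as well as change over time". Section D (Procedures) schedules four assessments, the first before Session 1, so baseline is presumably one of the repeated responses. Nothing says whether the arms share a baseline mean, whether baseline is a covariate, or how the post-treatment level contrast uses it.

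Specific Aim 2 says "We will conduct similar analyses to Aim 1, using both GLMs and GLMMs to obtain effect size estimates". Its GLMs predict the mediators "from baseline to post-treatment (controlling for baseline levels", and the exploratory GLM mediation also controls for baseline. The Aim 2 GLMMs, however, are referred back to the Aim 1 description, which is silent on this.

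**Site.** Section A places the trial in Seattle and Columbus. The randomisation text in Sections A and D gives a 1:1 ratio for individuals or clusters of up to three, and mentions neither site nor stratification. Section G says "We will examine associations between primary dependent variables and factors such as gender, age, time since trauma, etc. and make appropriate analytic adjustments", which does not name site. It also says "we will co-vary treatment group using dummy codes in all analyses", and Aim 1 adds random intercepts for treatment group and randomisation cluster. None of these is a site term.

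**Power.** Section F claims power of .80 at α = .05 for "moderate to large effects of condition on outcomes at post-treatment ($d = 0.72$) with 30 per group", allowing 20% dropout. No baseline-post correlation is given.

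**The concern.** The primary outcome has a less explicit baseline rule than the mediators. Two analysts could follow the Aim 1 sentence and obtain different estimates with different precision. The default reading of a treatment-by-time GLMM leaves the arm means free at baseline. The change contrast is then close to a change-score comparison, and the level contrast is not adjusted for a chance baseline difference. With about 24 completers per arm, that can decide whether the planned power survives the planned dropout.

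Site is similar but smaller. In a trial of 60 with no stated stratification, the arms can differ by chance in their share of each city. The treatment-group terms exist only in the active arm, so they cannot adjust the arm comparison for city.

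**Working it through.** **Inputs from the documents.** 30 per arm; 20% dropout, so 30 × 0.8 = 24 post-treatment scores per arm; α = .05; power .80; d = 0.72.

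**Assumptions.** Two-sided test; outcome SD 1 at both times; identity link; baseline-post correlation r = 0.3, 0.5 or 0.7; all 30 baselines kept; clustering ignored.

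**The plan's own figure.** The two-sided normal approximation at 30 per arm with no dropout gives (1.960 + 0.842) × √(2/30) = 0.723, close to 0.72. A one-sided test at 24 per arm gives (1.645 + 0.842) × √(2/24) = 0.718. A two-sided baseline-adjusted comparison at 24 per arm and r = 0.5 gives 0.716. Three routes fit, so the figure does not identify a baseline rule.

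**Variance of the treatment contrast.**
- Adjusted, or common baseline mean: 2(1 − r²)/24.
- Free baselines, change: 2[(1 − r²)/24 + (1 − r)²/30].
- Free baselines, post-treatment level: 2[(1 − r²)/24 + r²/30].

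Dividing by the first line, the ratio is 1 + 0.8(1 − r)/(1 + r) for change and 1 + 0.8r²/(1 − r²) for level.

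| | r = 0.3 | r = 0.5 | r = 0.7 |
|---|---|---|---|
| SE, adjusted | 0.275 | 0.250 | 0.206 |
| SE, free, change | 0.329 | 0.281 | 0.220 |
| SE, free, level | 0.286 | 0.281 | 0.274 |
| Extra variance, change | 43% | 27% | 14% |
| Extra variance, level | 8% | 27% | 77% |
| Power at d = 0.72, adjusted | 72.5% | 80.5% | 92.7% |
| Power at d = 0.72, free, change | 57.1% | 70.7% | 89.3% |
| Power at d = 0.72, free, level | 69.3% | 70.7% | 72.9% |

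Power is from the noncentral t distribution with noncentrality 0.72/SE and 45 or 46 degrees of freedom.

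**Site: chance of imbalance.** With 60 individuals in fixed 30:30 arms, the hypergeometric probability that the arms differ by at least 20 points in site share is 20%, 17% or 7% for an assumed site split of 30:30, 40:20 or 45:15. In simulations with 30:30 sites and blocks of four units, the probability is 20/27/37% without site stratification and 0/1/3% with it. The three figures are for all singles, an 80-10-10 mix of unit sizes 1 to 3, and equal thirds.

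**Site: size of shift.** Assume 18/30 against 12/30 from one city (20 points), complete data, and a 0.5 SD site difference. The raw shift is 0.2 × 0.5 = 0.10 SD.
- Site difference present at both times: the free-baseline change contrast shifts by 0 and the free-baseline level contrast by 0.10. The common-baseline contrast shifts by 0.10(1 − r) = 0.07/0.05/0.03.
- Site difference only at post-treatment: all three shift by 0.10. In the common-baseline model, a site main effect alone leaves 0.066/0.076/0.086; site plus site-by-time leaves 0.

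For comparison, the adjusted SE is 0.21 to 0.28.

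**Cost of site terms.** A 20-point imbalance multiplies the variance by 1/(1 − 0.2²) = 1.042. Detectable d rises from 0.7885/0.7158/0.5903 to 0.8051/0.7309/0.6027, an increase of 0.017/0.015/0.012.

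**The case against.** The strongest reply is that nothing here is wrong. A free-baseline treatment-by-time model is standard and valid in a randomised trial, and the four-assessment schedule makes baseline a response. Adjustment may also be intended, since Aim 2 describes baseline-controlled GLMs among analyses similar to Aim 1. All of that stands. What remains is an unstated rule and avoidable imprecision.

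A reader might infer more than the documents support:

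- *That the treatment estimate is biased.* It is not. Free baselines and chance site imbalance both add variance, and with site omitted its variance sits in the residual, so ordinary standard errors largely reflect it.
- *That the primary contrast needs 14% to 43% more participants.* That range is for change only. Aim 1 names level and change without ranking them, and the loss for level runs the other way in r.
- *That d = 0.72 shows adjustment was planned, or was not.* Three routes reproduce it, and Section F does not state sidedness.
- *That a 20-point imbalance always costs 0.2 SD per SD of site effect.* That holds only for a site effect that appears after baseline, or for the unadjusted level contrast.
- *That site is excluded.* It is unstated; the open list in Section G could admit it.
- *That the open covariate list inflates error.* No harm was shown: a fixed association rule held type I error at 4.6% to 5.0%.

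Two further objections stand and limit the remedy. A common baseline mean is safe only if baseline is answered before allocation is known, and Section D says only that it precedes Session 1. The constraint also makes the estimate sensitive to a stable site difference, which the free change contrast is not, so the site terms must accompany it.

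**Conclusion.** The point holds as a loss of precision in an under-specified primary model, and the sponsor should act on it. Free baselines raise the variance by 14% to 43% for change and 8% to 77% for level across assumed correlations of 0.3 to 0.7. At r = 0.5, power at d = 0.72 is 80.5% with adjustment and 70.7% without, for either contrast. Site is secondary: at most about 0.10 SD at an assumed 20-point imbalance and 0.5 SD site effect, which is below the SE.

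The correlation, site split, site effect and unit-size mix are not in the documents. All power figures ignore clustering and would be lower if outcomes correlate within groups. Confidence is medium.

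**What to change.** Add to Specific Aim 1, Analyses:

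> In the pre-post and four-point treatment-effect GLMMs of Aims 1 and 2, baseline is a response, time is coded 0 at baseline and the treatment main effect is omitted, so that the arms share one baseline mean. Site and site-by-time are fixed effects. GLMs of treatment effects include the baseline value of the outcome and site.

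This is conditional on the baseline questionnaire being completed before allocation is known. Make that order part of the procedure in Section D; if it cannot be assured, do not impose the common baseline mean. Leave the exploratory mediation models outside this rule.

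If randomisation has not begun, stratify the list by site. If it has, fix the model terms before outcomes are analysed.

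**Cost.** SAP wording, possibly a revised list, one or two degrees of freedom, and up to about 0.017 in detectable d if site is imbalanced by 20 points. The cost allowing for clustering was not computed and matters here, because the plan expects few treatment groups. The mismatch between group dummy codes (Section G) and group random intercepts (Aim 1) is a separate point; this change does not resolve it.

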Male and female lay leaders will be selected based on being a community leader, having a heart for healing and reconciliation in the Somali community, and willingness to later train additional group leaders. Lay leaders will be able to speak and read in both Somali and English. All lay leaders will sign contracts to be individual investigators affiliated with their respective universities. Lay leaders will attend two, 4-hour training sessions (approximately 6 hours actual training, allowing time for arrival and prayer times), where they will receive the manual and an overview of the program, review and practice components of group sessions, and identify potential issues and problem solve. Lay leaders will be volunteers.

Group participants will be recruited through flyers and word of mouth by the lay leaders, community and faith leaders, and self-referral, focusing on those in need of trauma healing based on their report of re-experiencing and/or avoidance of traumatic events. All participants will sign informed consent forms, in either Somali or English depending on their language preference. Randomization to active or waitlist will be conducted using a 1:1 ratio, allowing for individuals or clusters of up to three individuals being randomized as a unit. Questionnaires will be completed prior to the start of group (Session 1), middle (Session 3), and end (Session 6), with a three-month follow up for individuals in the RCT using a Qualtrics link. Participants will receive fifty dollars at the three-month follow up. Groups will meet weekly for 2 hours, with length of time varying depending on breaks for prayer. After each group, lay leaders will meet briefly with a clinical supervisor from the investigational team, either in person or on phone/online, for a discussion of the session, consultation on content or clinical issues that arose during session, and any supervisory notes. Once the six weekly sessions have been completed, a group social event will be held as a closure ceremony and to facilitate community reconciliation. The content of each group session is clearly delineated in the Islamic Trauma Healing manual.

E. Quality Control

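### Two-visit analyses omit the Session 3 scores, no model is named as primary for the post-treatment effect, and dropout related to Session 3 response that differs by arm would bias them

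*Combined protocol and SAP*

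**What the plan says.** Section D (Procedures) has questionnaires completed before Session 1, at Session 3, at Session 6 and at three months.

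- **Specific Aim 1, Analyses:** "We will compare pre-post GLMMs with those using data from all four time points to estimate the effects of treatment". The sentence goes on to name two targets, post-treatment level and change over time. It does not allot a model to each, and it names no primary model.
- **Specific Aim 2, Analyses:** "In the GLMs, treatment will predict negative beliefs, connectedness, and forgiveness from baseline to post-treatment", adjusted for baseline. GLMMs are planned alongside and are also to predict post-treatment levels.
- **Section G (Analytic Strategy):** pattern-mixture models are to judge whether missingness is ignorable. Then: "For non-ignorable missing data, values will be multiply imputed". No imputation is described for missingness judged ignorable.
- **Section F (Power Analysis):** "With a conservative estimated dropout of 20% across conditions, though no dropout occurred in our pilot work". Power is given separately for "outcomes at post-treatment ($d = 0.72$) with 30 per group" and for change over time: "For repeated measures analyses, with 4 data points, 30 per group with 20% missing data".

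**The concern.** A model with only Session 1 and Session 6 is valid when missing Session 6 scores depend on nothing beyond baseline and arm. If people leave because of how they were doing at Session 3, the data are missing at random given Session 3, but not given baseline alone. Session 3 is measured, so such dropout could well be judged ignorable. Imputation would then not be triggered, and the two-visit models would go uncorrected although the information needed is in hand.

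Two estimates of the primary effect could therefore differ for this reason, with no rule for choosing between them. Differential leaving is plausible: only the active arm attends weekly two-hour groups with an adapted form of imaginal exposure, and the plan itself intends to compare dropout between arms.

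**Working it through.** **The plan's own figure.** With 30 per arm and 20% loss, 24 per arm remain (12 of 60 people lost). The detectable effect by the normal approximation is (z for alpha + z for power) × √(2/n).

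- One-sided 0.05, n = 24: (1.645 + 0.842) × √(2/24) = 0.718.
- Two-sided 0.05, n = 24: (1.960 + 0.842) × √(2/24) = 0.809.
- Two-sided 0.05, n = 30: (1.960 + 0.842) × √(2/30) = 0.723.

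So 0.72 is reproduced as a post-treatment comparison, either one-sided after dropout or two-sided without it. The documents state no sidedness. That is a separate matter, but the calculation shows the scale of effect at issue.

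**Inputs for the bias.** From the documents: 30 per arm, 20% loss and the visit times. Assumed, because the documents give no values:

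- correlations S1–S3 0.6, S3–S6 0.7 and S1–S6 0.5;
- true effects of 0.35 SD at Session 3 and 0.70 SD at Session 6, in favour of the programme;
- logistic dropout on the Session 3 score, odds ratio 2 to 5 per SD;
- all loss after Session 3, and no clustering.

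**Mechanism.** The slope of Session 6 on Session 3, given baseline, is (0.7 − 0.6 × 0.5) / (1 − 0.6²) = 0.40 / 0.64 = 0.625. The bias of the two-visit contrast is about 0.625 times the arm difference in how far completers' baseline-adjusted Session 3 mean has moved from that of their whole arm. A bias of 0.05 to 0.15 SD thus needs a differential shift of 0.05 / 0.625 = 0.08 to 0.15 / 0.625 = 0.24 SD. If the shift is the same in both arms, it cancels.

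**Simulated estimates (large samples, true effect 0.70).** The two-visit estimate is Session 6 adjusted for baseline among completers.

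| Loss, active / waitlist | Dropout depends on Session 3 in | Two-visit estimate |
|---|---|---|
| 20% / 20% | active arm only, odds ratio 2–5 | 0.75 to 0.80 |
| 30% / 10% | active arm only, odds ratio 2–5 | 0.77 to 0.84 |
| 30% / 10% | both arms, odds ratio 2 | 0.75 |
| 20% / 20% | both arms alike | 0.70 |
| 20% / 20% | waitlist only, odds ratio 2–5 | 0.60 to 0.65 |

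An estimate that also uses Session 3 for everyone stays at about 0.70.

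**Sensitivity to the correlations.** A second set used correlations of 0.7, 0.8 and 0.65, a true effect of 0.72 and log-odds slopes of 1 to 2 per SD. The two-visit estimate was 0.78 to 0.83 when only active-arm dropout depended on Session 3, about 0.72 when both arms were alike (slope 1), and 0.65 to 0.66 when only the waitlist's did (slope 1). Estimates using Session 3 were 0.715 to 0.724.

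**Against sampling error.** With an S1–S6 correlation of 0.5 and 24 per arm, the standard error is √(2 × (1 − 0.25) / 24) = 0.25 SD. A bias of 0.05 to 0.15 SD is 0.2 to 0.6 of a standard error. Using Session 3 lowers the standard error by only about 1 to 5%.

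**The case against.** The best reply is that the plan already holds the remedy. The Aim 1 sentence also plans four-time-point GLMMs, which use Session 3 and can be read as estimating post-treatment level. Aim 2 says outright that its GLMMs predict post-treatment levels. A reader might infer that Session 3 is left out of the primary-outcome analysis altogether; the documents do not support that. The separate power figures for level and for change make it plausible that the pre-post model is the level analysis, but nothing states it. What stands is that two candidate estimates exist with no primary and no rule if they differ. Nor is time specified as categorical in the four-point model, so its Session 6 contrast is undefined.

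A reader might also infer that someone who leaves after Session 3 contributes nothing. That is true of the Aim 2 GLMs without imputation. In a pre-post mixed model with baseline as an outcome row, the baseline still counts. Keeping that row does not remove the bias, however: in simulation such a model was equally biased.

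The plan has other safeguards: pattern-mixture models, conditional imputation, and comparison of dropout rates, reasons and dropouts' symptoms. They look at the right problem, but they would have little power with about 12 leavers. The dropout comparisons describe the loss without correcting the estimate.

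Finally, the sizes are generous. Anyone who leaves before Session 3 gains nothing from the fix, and the simulations treat leaving the group as missing the Session 6 questionnaire, which the documents do not say. Both points stand.

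**Conclusion.** The point holds in a conditional form. The two-visit analyses are exposed to an avoidable bias that the missing-data plan need not correct, and the plan does not say whether the Aim 1 post-treatment result rests on them. Under the stated assumptions the bias is roughly 0.05 to 0.15 SD in the programme's favour (7 to 21% of 0.70) if active-arm poor responders leave selectively or more often. It is about zero if both arms lose them alike, and about 0.05 to 0.10 SD against the programme if only the waitlist does.

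It would be tempting to conclude that the effect will be overstated. The documents do not support a direction: they assume 20% loss across conditions, give no differential rate, and report no dropout in the pilot. The sizes rest on assumed correlations and dropout models, and are upper-end because all loss falls after Session 3. They are modest beside a standard error of about 0.25 SD, but the correction is cheap and should be made.

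**What to change.** In Specific Aim 1, name as the primary estimate the Session 6 treatment contrast from one likelihood-based model that includes Session 3, with visit as a category, treatment-by-visit terms and the planned clustering terms. Keep the pre-post GLMM as a sensitivity analysis only.

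For the Aim 2 GLMs, impute missing Session 6 values under missing at random, separately by arm, with Session 3 values in the imputation model. Do this whatever the ignorability check shows.

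The cost is a change of wording in the Aim 1, Aim 2 and Analytic Strategy sections and a little more analysis work. No new data or visits are needed. Someone who leaves before Session 3 is not helped by the change, and dropout that depends on the unseen Session 6 score itself would still need the planned pattern-mixture work.

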Islahul Qulub: Islamic Trauma Healing. Several years of iterative, collaborative development work with the Somali community have guided the content and format of the Islamic Trauma Healing program. A manual for the program was developed (Lang, Zoellner, Graham, Marks, & Feeny, 2016), and a local Imam carefully reviewed the content of the manual. Focus group feedback from lay leaders and group members was also utilized in revisions. The program was designed for groups of 5-7 members, with two lay leaders of the same gender. The program is structured so that the lay leader training, comprised of two 4-hour trainings, focuses on teaching lay leaders the skills of discussion leading, with the manual content providing more of the direct therapeutic work. That is, the lay leaders are not explicitly taught how to be psychotherapists or how to do cognitive behavioral therapy specifically. The manual contains an introduction to trauma healing, including a description of types of trauma exposure and common reactions, as well as Islamic principles related to trauma healing. Session-by-session content is clearly spelled out in the manual. Each session includes time for community building rituals (e.g., sharing tea or coffee), spiritual preparation using a brief supplication written by the local Imam, prophet narratives relevant to trauma healing, and a brief closing supplication also written by the Imam. In the first session, a rationale for the program, common reactions to trauma, and a breathing relaxation exercise are described. Starting in the second session and continuing through the last session, talking individually to Allah about the trauma is conducted. In the last session, group members are encouraged to organize a closing event at which certificates of program completion are given.

The program is 6 sessions long. This duration is in line with evidence that very brief or shortened protocols (e.g., four 30 min sessions) can substantially reduce PTSD symptoms (Cicrang et al., 2011; van Minnen & Foa, 2006). Key components of the program are prophet narratives aimed at targeting trauma-

related beliefs, and talking to Allah, aimed at targeting trauma memories.

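### The post-treatment test in Aim 1 uses a random intercept estimated from about 4-6 therapy groups with no small-sample correction, and the dummy codes prescribed elsewhere in the plan do not solve the problem

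*Combined protocol and SAP*

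**What the plan says.** The combined protocol and SAP gives two rules for therapy-group clustering.

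- **Specific Aim 1, Analyses.** In the generalized linear mixed models, "we will include random intercepts for both treatment group and cluster (for those choosing to be randomized in a cluster"). The intercepts apply only to people who are in a therapy group or a randomization cluster. The models are to estimate both the post-treatment level and change over time. PS-SR-5 is the primary outcome. The Aim 2 analyses refer back to this approach.
- **G. Analytic Strategy.** Therapy group is to be entered as dummy codes in all analyses, on the ground that "linear mixed models are difficult to estimate when the number of clusters is very small".

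The number of therapy groups is not stated. Section B says that "The program was designed for groups of 5-7 members", and section F says that "we will recruit 30 individuals per treatment group". Neither G nor the Aim 1 and Aim 2 sections name an estimator (ML or REML), a reference distribution, a degrees-of-freedom method or a small-sample correction. No ICC is given.

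**The concern.** A random-intercept model for the active arm is a reasonable way to allow for therapy groups, but here the between-group variance must be learned from about five groups. Three things then go wrong together if a large-sample test is used. ML understates the between-group variance. The estimate is often set to zero, so the standard error loses its allowance for groups. And a z reference ignores that the active-arm part of the standard error rests on only 3-5 degrees of freedom. The p-value and interval for the post-treatment difference are then too favourable in the very case that the intercept is meant to handle.

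Section G shows that the authors know the difficulty, but its answer is a different model. The plan leaves open which model governs. An analyst could choose after seeing the data, and both options carry an inflated error rate when groups differ.

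**Working it through.** **Inputs.** From the documents: α = 0.05, 30 per arm, 20% dropout (24 completers per arm), groups of 5-7. Assumed: a two-sided test (sidedness is not stated) and a group ICC ρ of 0 to 0.20.

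**The plan's own figure.** The plan gives no type I error under clustering. Its nearest figure is the detectable difference d = 0.72, which follows from formulas for independent observations:

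- one-sided, 24 per arm: (1.645 + 0.842) × √(2/24) = 0.718;
- two-sided, 30 per arm: (1.960 + 0.842) × √(2/30) = 0.723.

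Two-sided with 24 per arm gives 2.802 × √(2/24) = 0.809. The stated figure can therefore be reached without any allowance for therapy groups, and it does not settle how the test will be done.

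**Number of groups.** 30/7 = 4.3 and 30/5 = 6, so about 4-6.

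**Hand check: J = 5 groups of m = 6 against 30 waitlist, ρ = 0.10, total variance 1.**

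1. Active-arm variance: [1 + (m − 1)ρ]/30 = 1.5/30 = 0.0500. Waitlist variance: 1/30 = 0.0333. Sum: 0.0833.
2. Satterthwaite degrees of freedom: 0.0833² / (0.0500²/4 + 0.0333²/29) = 0.006944/0.000663 = 10.5. The 5% critical value is 2.21, against 1.96 for z. Using 1.96 with 10.5 degrees of freedom gives an error of about 7.7% before any truncation of the variance at zero. Truncation raises the average REML variance estimate and so lowers this somewhat.
3. REML sets the group variance to zero when the between-group mean square is no larger than the within-group one. That has probability P(F with 4 and 25 df ≤ (1 − ρ)/(1 + 5ρ)) = P(F ≤ 0.9/1.5 = 0.6), about 33%.
4. Group dummies (average of the groups against waitlist): the residual variance is (25 × 0.9 + 29)/54 = 0.954, so the model variance is 0.954 × 2/30 = 0.0636 against a true 0.0833, a ratio of 1.31. With 54 df the critical value 2.005 acts like 2.005/√1.31 = 1.75, an error of about 8.6%.

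**Simulation under no effect**, same layout, 400,000 trials per scenario, nominal 5%:

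| Assumed ICC | 0 | 0.05 | 0.10 | 0.20 |
|---|---|---|---|---|
| Random intercept, ML, z | 5.3% | 6.4% | 7.3% | 8.9% |
| Random intercept, REML, z | 4.6% | 5.5% | 6.2% | 7.4% |
| Group dummy codes | 5.0% | 6.7% | 8.6% | 12.4% |
| Groups ignored | 5.0% | 6.5% | 8.0% | 11.0% |

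Varying the layout over 4, 5 and 6 groups of 5-6 against 24-30 waitlist (15,000 trials per cell), at ICC 0.05 / 0.10 / 0.20:

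- ML with z: 6.3-6.5 / 7.1-7.8 / 7.9-9.7%;
- REML with z: 5.2-5.6 / 6.0-6.6 / 6.8-7.8%;
- REML with Satterthwaite degrees of freedom: 3.9-4.5 / 4.4-4.9 / 4.9-5.2%.

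Adding randomization clusters of 1-3 with an assumed ICC of 0.1 gives, at group ICC 0.10 / 0.20, 8.2 / 9.3% for ML with z and 6.9 / 7.7% for REML with z.

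**The case against.** The strongest reply is that section G already deals with few clusters. If it governs, no therapy-group variance is estimated and the z-test figures do not arise. That is fair as a reading of G, but it does not rescue the test. A full set of group dummies is collinear with treatment. If the contrast is instead taken as the average of the groups against waitlist, the error is about 7-12% once the groups are seen as a sample of groups that could have been formed. The case for dummies is sound only if inference is limited to these particular groups, and the plan does not say so.

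The second reply is that the inflation depends on assumptions. This stands. A reader might infer that the planned test has a 6-10% error rate outright. The documents do not support that: the range needs ML, a z reference and an ICC of at least 0.05, and the plan commits to none of these. With REML the excess is at most about three percentage points, and with no group differences there is essentially none.

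The third reply concerns scope. A reader might infer that every mixed model in Aims 1 and 2 is too favourable by these amounts. That does not follow. Only a single post-treatment contrast was simulated, without baseline data. A group intercept that is constant over time cancels from within-person change, so the change-over-time tests raise a different question that these figures do not answer.

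Finally, the number of groups is inferred from the design size; two sites and same-gender leaders make the real count uncertain.

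**Conclusion.** The point holds for the post-treatment level. Aim 1 specifies a therapy-group intercept from about 4-6 groups with no small-sample correction, section G specifies something incompatible, and either route can exceed 5% when groups differ. Over an assumed ICC of 0.05-0.20 the error is about 6-10% (ML, z), 5-8% (REML, z) or 7-12% (dummy codes). At ICC 0 all are near nominal.

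The inflation is moderate and conditional. It still merits a change, because it bears on the primary outcome, a standard method brings the error back to about 5% or below, and the plan's silence leaves the choice of model and test to be made after the data are in.

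**What to change.** Reconcile section G with the Aim 1 analysis, as follows:

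1. Remove the therapy-group dummy codes from these models. If they stayed, a random intercept for the same groups would have no between-group variation left to estimate.
2. Fit the post-treatment models for PS-SR-5 and the other continuous scores as linear mixed models by REML, with the therapy-group intercept for the active arm.
3. Keep that intercept in the model whatever its estimated size.
4. Test treatment, and form its interval, with Satterthwaite or Kenward-Roger degrees of freedom.

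The cost is a short edit to two sections and a software option; recruitment, treatment and data collection are untouched. The downside is small: if groups truly do not differ, the test is somewhat conservative (type I error about 2.5-3.7%) and the interval slightly wider. In the layout above at ICC 0 the degrees of freedom are (2/30)² / [(1/30)²/4 + (1/30)²/29] = 14.1, so the critical value is 2.14 instead of 1.96 and the interval is about 9% wider (2.14/1.96 = 1.09).
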